4.4. General Considerations

- Venetoclax must be administered with food
- Prevention of infection
 - o Prophylactic antibiotics may be given with each course until neutrophil recovery to $500/\mu L$ or greater
 - Suggestions include: Levaquin 500 mg orally daily (or other appropriate antibacterial agent); caspofungin or other appropriate antifungal agent; valacyclovir 500 mg orally daily or acyclovir 200 mg orally twice daily or other appropriate antiviral agent.
- Prevention and treatment of CNS disease
 - 8 prophylactic IT chemotherapy treatments are recommended. However, if the patient has had prior IT therapy, number of IT chemotherapy can be

- reduced if thought by the treating physician to be in the best interest of the patient after discussion with the PI.
- For patients with active CNS disease, consider methotrexate alternating with cytarabine twice weekly until CSF clear; then once weekly for 4 weeks, then back to prophylactic schedule. Consider XRT to the base of the skull, particularly with cranial nerve root involvement (cranial nerve palsies). Modifications to the regimen thought to be necessary for administration of XRT are allowed after discussion with the Pl.
- Venetoclax will provided by the Abbvie through the MDACC pharmacy. Ponatinib is indicated for the disease setting and will be charged to the patient/insurance.

4.5. Suggested Standard Dose Reductions/Modifications:

- Venetoclax
 - o Moderate and strong CYP3A inducers and inhibitors are discouraged during venetoclax administraton. If a patient requires use of CYP3A inducers, use with caution. In many instances, such as antifungal prophylaxis with "azole" therapy in neutropenic patients, CYP3A inhibitors are required in ALL patients. Venetoclax should be administered at 50% dose reduction in the setting of moderate CYP3A inhibitors (i.e. isavuconazole, ciprofloxacin, diltiazem), and 75% dose reduction in the setting of strong CYP3A inhibitors (i.e. voriconazole), with the exception of posaconazole in which dose reduction should be approximately 83% (e.g. dose reduction to 70mg if patient would normally be taking 400mg). The venetoclax dose reduction should continue for the duration of co-administration. In the event the co-administered CYP3A inhibitor is discontinued, the assigned venetoclax dose should be resumed 2-3 days after discontinuation. During the venetoclax ramp-up, these agents must be held; however, they may be started or resumed 24 hours after the highest planned dose of venetoclax is given, along with the appropriate dose reduction of venetoclax as above.
 - o Non-hematological toxicity If grade 3 or 4 non-hematologic toxicity is attributable to venetoclax, dose interruption of venetoclax is required. Patients who experience drug-related grade 3 non-hematological toxicity may be given a subsequent course one dose level below the previous course, but the patient must have recovered to grade ≤1 before start of the next course. If a patient has drug-related grade 4 non-hematological toxicity, he/she may receive a subsequent course at one reduced dose level after resolution of toxicity to grade ≤1, only if approved by the PI based on the clinical significance of the toxicity and only if patient has had derived a benefit from the therapy. The dose of venetoclax can be decreased during a cycle, at the discretion of treating physician and PI, for chronic grade 2 non-hematological toxicity. Other dose modifications may be considered as clinically indicated with documentation and approval of the PI. The dose reduction guidelines for venetoclax are in the table below:

Current Venetoclax	Reduced Dose
Dose	
800mg	400mg
400mg	200mg
200mg	100mg
100mg	50mg
50mg	20mg

20mg	Hold venetoclax
------	-----------------

o Hematologic toxicity

- Dose interruptions or modifications will be made for grade 4 hematological toxicities unless it is assessed to be due to the underlying disease. Patients with baseline neutropenia or those who have significant bone marrow involvement may be particularly at high risk.
- If a subject achieves CRi or has a morphologically leukemia free bone marrow after completion a cycle, venetoclax should be interrupted for up to 14 days after the last day of the cycle or until recovery of ANC >500/µL.
- If a subject presents with new onset grade 4 during subsequent cycles, unless it is thought to be due to the underlying disease, venetoclax dosing should be interrupted until ANC recovery to >500/µL. Subsequent dosing should be in consultation with the study PI. For the first episode of grade 4 hematologic toxicity the dose of venetoclax may be reduced; however for subsequent episodes of grade 4 hematologic toxicity (not attributed to the underlying disease), the dose of venetoclax should be reduced. The dose reduction guidelines for venetoclax are in the table above (same as for non-hematologic toxicity).

Ponatinib

o The following table provides dose reduction guidelines for ponatinib

Current Ponatinib Dose	Reduced Dose
45mg	30mg
30mg	15mg
15mg	Hold ponatinib

o Hematologic toxicity

- Cytopenias are common in the patient population studied in this trial.
 Dose modification for ponatinib for hematologic toxicities will be made unless attributed to the underlying leukemia, after appropriate dose reductions of venetoclax have been made, as above.
- No dose modifications are required for grade 1-2 hematologic toxicity or for grade 3-4 hematologic toxicity attributed to underlying leukemia.
- For grade 4 hematologic toxicity occurring despite venetoclax dose interruption of ≥1 week, ponatinib should be held until recovery of ANC to ≥1.5 x 10⁹/L and platelets ≥75 x 10⁹/L, and then resumed at one dose level reduction.
- o Grade II transaminase elevation
 - Hold until grade I or less.
 - After resolution to grade I or less, ponatinib may be resumed but must be reduced by one dose level.

o Other liver function abnormalities

- For patients who develop AST or ALT of >=3x ULN and a total bilirubin of >2 x ULN with alkaline phosphatase of <2 x ULN while on treatment, ponatinib should be discontinued. Investigation of other causes of liver abnormalities (e.g. azoles) is recommended.
- o Pancreatitis

- If asymptomatic grade 1-2 lipase elevation, ponatinib may be held or dose reduced at the discretion of the PI. If held, it should be dose reduced when resumed.
- If asymptomatic radiologic pancreatitis (grade 2 pancreatitis), asymptomatic grade 3-4 lipase elevation, or symptomatic grade 3 pancreatitis, hold ponatinib until grade 1, then dose reduce by one dose level
- If grade 4, discontinue ponatinib
- o Arterial or venous thrombosis
 - For patients with arterial thrombosis, ponatinib should be discontinued.
 - For patients with pulmonary embolism or lower extremity deep venous thrombosis, ponatinib should be dose reduced (one dose level) or discontinued.
 - For patients with superficial venous thrombosis or line-associated upper extremity deep venous thrombosis, ponatinib may be continued at the same dose, although holding dose and/or dose reduction (one dose level) can be considered at the discretion of the treating physician according to the assessment of the patient's best interest.

Heart failure

- If grade 1-2, hold ponatinib until resolution then resume at same dose
- If grade 3, hold ponatinib until grade 1 or resolved, then reduce dose by one dose level
- If grade 4, discontinue ponatinib
- Hemorrhage or fluid retention (edema)
 - If grade 3-4, hold ponatinib until grade I or less, then reduce dose by one dose level.
- Grade III-IV non-hematological toxicity (excluding specific toxicities listed above) attributed to ponatinib:
 - Hold until grade I or less.
 - Ponatinib may be resumed at one dose level reduction after resolution to grade I or less, if resolves within 4 weeks of discontinuation. If the same grade III-IV toxicity recurs, ponatinib should be discontinued.
- o Major surgery
 - Ponatinib should be held for at least 1 week prior to any planned major surgery, as determined by the PI.

Dexamethasone

- Dose should remain at 40mg unless grade 3 or 4 steroid myopathy or other significant toxicity occurs.
- For grade 3 or higher pancreatitis, dexamethasone should be held until resolved to grade 1 or less, after which it may be resumed at the same dose.
- For other grade 3 or 4 toxicities attributed to dexamethasone, dexamethasone should be held until resolved to grade 1 or less, after which it may be resumed at the same dose or dose reduced (at the discretion of the PI).
- o Dexamethasone is not required to be dose-adjusted for hyperglycemia.
- o If dose reductions of dexamethasone are performed, guidelines are in the table below:

Current Dexamethasone Dose	Reduced Dose
40mg	20mg
20mg	10mg
10mg	Hold dexamethasone

 Further reductions beyond what is shown in the table above may be allowed if recommended by the treating physician and after discussion with the PI.

4.6 Prophylaxis and Management of TLS

- There is a potential for TLS, especially in those with elevated pretreatment LDH levels, elevated leukocyte count, renal dysfunction, and dehydration. To mitigate the risk for TLS, subjects will receive tumor lysis prophylaxis, including hydration (e.g., oral, intravenous) and treatment with an agent to reduce the uric acid level (e.g., allopurinol, rasburicase) prior to and during the inpatient portion of cycle 1. For subjects who had dose delay or interruptions, TLS prophylactic measures may need to be implemented based on the disease status prior to resuming treatment. TLS prophylaxis must be initiated in all such subjects prior to the first venetoclax dose or first new escalated dose.
- Cycle 1
 - Hospitalization (required) starting the night before the initial dose of venetoclax for cycle 1 and for up until 24 hours after reaching the target dose (day 12-14 for patients without recent ponatinib exposure or day 5-7 for patients with recent ponatinib exposure, depending on the dose level)
 - An oral agent to reduce the uric acid level (e.g., allopurinol or substitute) must be initiated prior to first venetoclax dose. Subjects allergic to or otherwise unable to receive allopurinol must use another uric acid reducer or rasburicase prior to venetoclax dosing.
 - Intravenous hydration must be started upon admission (i.e. the day prior to initiation of venetoclax) at a rate as clinically appropriate and will continue throughout the hospitalization. Urine output must be monitored. Diuretics may be used per investigator discretion.
 - TLS chemistry tests (calcium, phosphorus, potassium, uric acid, and creatinine) on the first day of venetoclax and each day of a new dose within 6 hours (+/-2 hours prior to venetoclax dosing. TLS chemistries should also be checked 6 hours after (+/-2 hours) after the first dose or new dose level.
 - TLS chemistry test results (calcium, inorganic phosphorus, potassium, uric acid, and creatinine) must be reviewed by the investigator in real time and prior to the subject's next dose to ensure appropriate subject management.
 - If a subject meets criteria for clinically significant laboratory or clinical TLS, no additional venetoclax dose should be administered until resolution.

Cycles 2+

- If any laboratory changes are noted in cycle 1, and deemed clinically significant for TLS by the investigator, no additional venetoclax doses should be administered until resolution. TLS prophylaxis may need to be continued with subsequent cycles based on the ongoing risk of development of TLS.
- Drug interruption for up to 48 hours following transient chemical changes and laboratory TLS may be allowed and will not require a dose reduction. If the TLS has not resolved within 48 hours, then the dose should be reduced.
- 4.7 Completion of Phase I The phase I portion will define the DLTs, MTD and RP2D of
 the combination treatment. Dose escalation will proceed in standard '3+3' design (see
 Statistical Methods section). Once the MTD is established (or if the MTD is not reached with
 800 mg of venetoclax), the phase II portion of the study will commence.

• 4.8 Definition of DLT -

A DLT will be defined as any of the following adverse events that cannot be considered primarily related to the underlying malignancy, or a comorbid condition, occurring:

- For patients without recent ponatinib exposure, between day 8 and day 35 of cycle 1 (with the exception of hematologic toxicity which may be assessed up to day 49 of cycle 1)
- For patients with recent ponatinib exposure, between day 1 and day 28 of cycle 1 (with the exception of hematologic toxicity which may be assessed up to day 42 of cycle 1)

Any ≥ grade 3 non-hematologic toxicity with the following exceptions:

- Grade 3 alopecia
- Grade 3 nausea, vomiting, diarrhea with electrolyte abnormalities lasting less than 48
 hours that are not clinically significant and that does not require total parenteral
 nutrition (TPN), tube-feeding, or hospitalization
- Infection, unless the infection resulted from unexpectedly complicated by the degree
 or duration of myelosuppression in the absence of persistent leukemia.

Patients who receive at least a full course of therapy will be considered to be evaluable for toxicity/DLT and will not be replaced unless the PI determines that further additional patients at that dose level are required for safety purposes.

Hematologic toxicity will be defined as:

- For patients without recent ponatinib exposure, failure to recover ANC > 500/μL or platelet count > 25,000/μL by day 49.
- For patients with recent ponatinib exposure, failure to recover ANC > 500/µL or platelet count > 25,000/µL by day 42.

This will be considered DLT. For patients with \geq 5% blasts, myelodysplastic changes, or evidence of disease by flow cytometry/cytogenetics, failure to recover neutrophil or platelet count may not be considered DLT as this could be the result of persistent disease.

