4. TREATMENT OF SUBJECTS

- 4.1. Variations in doses of the study agents or supportive care medications or dose schedules other than those suggested below are allowed if deemed to be in the best interest of patients. Such changes should be discussed with the principal investigator before they are instituted.
- 4.2. Treatment Overview The regimen consists of 4 cycles of induction/consolidation followed by up to 2 years of maintenance therapy for responding patients. For patients who have not received ponatinib within 2 weeks of the anticipated start date, the first cycle is 35 days, as single-agent ponatinib will be given for 7 consecutive days, after which venetoclax, ponatinib and corticosteroids will be given in combination. For patients who have received ponatinib within 2 weeks of the anticipated start date, the first cycle is 28 days, as the ponatinib single-agent lead-in will be omitted. For all patients, each consecutive cycle will be 28 days. Patients achieving remission will be referred to ASCT at the discretion of the treating physician, based on donor availability and suitability for ASCT. Patients will be removed from the study and will discontinue venetoclax at the time of ASCT. These patients will still be followed for survival analyses.
- **4.3** Cycle 1 (Induction) Patients who have not received ponatinib within 2 weeks of the anticipated start date will receive the following agents:
 - Ponatinib 45mg orally daily on days 1-35
 - Venetoclax orally in a daily dose escalation schema:

•							
		Day 8	Day 9	Day 10	Day 11	Day 12	Day 13-35
	Dose level -1 venetoclax	20 mg	50 mg	100 mg	200 mg	200 mg	200 mg
	Dose level 1 venetoclax (STARTING DOSE)	20 mg	50 mg	100 mg	200 mg	400 mg	400 mg
	Dose level 2 venetoclax	20 mg	50 mg	100 mg	200 mg	400 mg	800 mg

- Dexamethasone 40mg IV/PO on days 8-11
- CNS prophylaxis with methotrexate 12 mg intrathecally (IT) (6 mg via Ommaya reservoir) on day 9 (± 3 days) and cytarabine 100 mg IT on day 14 (± 3 days).
- For patients with CD20 expression (≥20% by flow cytometry), rituximab 375 mg/m² may be added at the discretion of the treating physician after the maximum dose of venetoclax has been reached. Rituximab will be given on day 14 (±3 days) and on day 21 (±3 days).

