Patients may receive ponatinib monotherapy on days 1-7 as an outpatient. Bone marrow will be performed on day 7 (±1 day) for correlative studies but must be prior to the initiation of venetoclax. Additional hydroxyurea or corticosteroids are allowed during the 7-day ponatinib lead-in after discussion with the PI.

Due to the potential for tumor lysis syndrome (see section 4.6), patients will be hospitalized the day prior to initiation of venetoclax and will remain hospitalized until 24 hours after the completion of the venetoclax dose escalation (day 12-14, depending on the dose level). Patients in both phase I and phase II cohorts will be hospitalized. Hospital stay may be

prolonged in patients with infections or other issues requiring inpatient stay. The remainder of the cycle can be administered as an outpatient. At the end of cycle 1, patients will have bone marrow aspirate/biopsy for response assessment.

For patients who have received ponatinib within 2 weeks of the anticipated start date, both venetoclax, ponatinib, and dexamethasone will be started on day 1 of the first cycle, and the 7-day lead-in of single-agent ponatinib will be omitted. Therefore, all days above will be moved forward 7 days, and the cycle will end on day 28.

4.3 Cycles 2-4 (Consolidation) – Patients will receive the following agents:

- Venetoclax orally at the maximum dose used in cycle 1, given daily on days 1-28
- Ponatinib orally daily on days 1-28. The dose of ponatinib will be adjusted according
 to the remission status as indicated by bone marrow assessment after cycle 1.
 - o Patients who have not received CR/CRi: 45mg daily
 - o Patients who have achieved CR/CRi but not CMR: 30mg daily
 - o Patients who have achieved CR/CRi with CMR: 15mg daily
- Dexamethasone 40mg orally daily on days 1-4
- CNS prophylaxis with methotrexate 12 mg IT (6 mg via Ommaya reservoir) on day 2 (± 3 days) and cytarabine 100 mg IT on day 7 (± 3 days).
- For patients with CD20 expression (≥20% by flow cytometry), rituximab 375 mg/m² may be added at the discretion of the treating physician. Up to 2 doses of rituximab may be given during each cycle.

All therapy can be administered in the outpatient setting. A total of 8 doses of IT chemotherapy are planned for cycles 1-4. A total of 8 doses of rituximab may be given for cycles 1-4. Any missed doses of rituximab or IT chemotherapy can be made up in subsequent cycles at the discretion of the treating physician.

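### Section 4.6 requires no TLS chemistry later than 4-8 hours after the first target dose of venetoclax, before the second full dose and discharge

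*Combined protocol and SAP*

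**What the plan says.** Section 4.3, Cycle 1 (Induction), gives "Venetoclax orally in a daily dose escalation schema", with a separate ramp-up for each of three dose levels.

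The Cycle 1 part of section 4.6 sets the chemistry schedule:

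- **Pre-dose draw:** due "on the first day of venetoclax and each day of a new dose within 6 hours" before dosing. The 2-hour tolerance that follows has an unclosed bracket, so the window can be read in two ways.
- **Post-dose draw:** "TLS chemistries should also be checked 6 hours after (+/-2 hours) after the first dose or new dose level".
- **Review:** results "must be reviewed by the investigator in real time" and before the next dose.
- **Hold rule:** for clinically significant laboratory TLS or clinical TLS, "no additional venetoclax dose should be administered until resolution".
- **Hospital stay:** from the night before the first dose and "for up until 24 hours after reaching the target dose". Section 4.3 says the same: patients "will remain hospitalized until 24 hours after the completion of the venetoclax dose escalation". It also states: "Patients in both phase I and phase II cohorts will be hospitalized". The rest of cycle 1 may be given to outpatients.
- **Other cover:** intravenous hydration continues throughout the stay, urine output is monitored, and a uric-acid-lowering agent is started before venetoclax.

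Two other sections bear on the point. Section 6.2, item 5, adds the same analytes weekly or more often in cycle 1, on no set day. Section 4.5 allows CYP3A inhibitors to start or resume 24 hours after the top ramp-up dose, with venetoclax reduced.

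**The concern.** Because both draws depend on a new dose, what each step receives depends on what happens the next day. After every lower step comes another increase, whose pre-dose draw also serves as a next-day check on the step before. After the first target dose comes the same dose again, which triggers no draw.

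Three decisions fall at that point: giving the second full dose, ending the required stay (and with it the mandated hydration), and starting or resuming a CYP3A inhibitor. The laboratory part of the hold rule needs a laboratory value. Laboratory TLS that appears after the 4-8 hour draw could go unseen at all three decisions.

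**Working it through.** **Inputs.** Ramp-up doses come from the table in section 4.3, Cycle 1. Draw rules and hospital-stay days come from section 4.6. Dosing every 24 hours is assumed.

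**Step 1: reproduce the plan's own figure.** Section 4.6 puts the end of the stay at day 12-14, or day 5-7 with recent ponatinib exposure. The end of stay is the first target-dose day plus 1. With recent ponatinib, subtract 7.

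| Level | Doses (mg) | New-dose days | First target dose | End of stay | With recent ponatinib |
|---|---|---|---|---|---|
| -1 | 20, 50, 100, 200 | 8-11 (4 steps) | day 11 | 11 + 1 = 12 | 12 - 7 = 5 |
| 1 | 20, 50, 100, 200, 400 | 8-12 (5 steps) | day 12 | 12 + 1 = 13 | 13 - 7 = 6 |
| 2 | 20, 50, 100, 200, 400, 800 | 8-13 (6 steps) | day 13 | 13 + 1 = 14 | 14 - 7 = 7 |

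The plan's range is reproduced. On the end-of-stay day the dose is unchanged, so neither draw rule applies.

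**Step 2: values after a lower step.**
- The post-dose draw falls at 6 - 2 = 4 to 6 + 2 = 8 hours.
- The next day's pre-dose draw is 4-8 hours before dosing if the window is read as 6 plus or minus 2. That is 24 - 8 = 16 to 24 - 4 = 20 hours after the previous dose.
- If the window is read as any time up to 8 hours before dosing, the draw is 16-24 hours after the previous dose.
- On either reading the last required value is at most 8 hours old when the next dose is due.

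**Step 3: values after the first target dose.**
- The post-dose draw is again at 4-8 hours, and no further draw is triggered.
- At the second full dose, and at the 24-hour discharge point, that value is 24 - 8 = 16 to 24 - 4 = 20 hours old.
- This holds at all three levels and on both cycle 1 schedules.

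**Step 4: size of the last step.**
- The increases are 20, 30, 50, 100, then 200 at levels 1 and 2, then 400 at level 2.
- The last is the largest in mg each time: 100/200 = 200/400 = 400/800 = 50% of the target dose.
- As a ratio it is 2-fold, no larger than earlier steps (50/20 = 2.5, then 2 throughout).

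**Step 5: do other provisions fill the gap?**
- The review sentence in 4.6 governs results already drawn. The 4-8 hour value satisfies it.
- The section 6.2 panel could fall on that morning by chance, or up to about 7 days later.
- Section 4.5 requires no chemistry before a CYP3A inhibitor. It does cut venetoclax by 50% (moderate inhibitors), 75% (strong) or about 83% (posaconazole; its example of 400 to 70 mg is 1 - 70/400 = 82.5%).

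**The case against.** Section 4.6 breaks no rule of its own. It applies one standard to every step: a value before each increase and another 4-8 hours after it. The target step meets that standard. Lower steps get a later value only as a by-product of the next increase, and the second full dose is not an increase. Any finite schedule has a last draw after which a change could be missed, and nothing in the documents makes 16-24 hours the right cut-off. The patient is in hospital, hydrated, with urine output monitored and a uric-acid-lowering agent started. Clinical TLS triggers the hold without a new draw, and 8, 10 or 12 panels have already been taken. Investigators may draw bloods that morning anyway. The CYP3A link is weak, because venetoclax is reduced at the same time.

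Much of this stands. There is no internal contradiction, the target step is not unmonitored, and the documents neither quantify late laboratory TLS nor say it is likelier at this step. The CYP3A part adds little risk that can be shown.

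It does not remove the point. A patient managed exactly as written can take a second full dose and leave mandated hydration with no chemistry later than 8 hours after the largest mg increase. The plan keeps the patient in hospital for up to 24 hours after the target dose, but schedules no chemistry at the end of that time and gives no reason for the omission. If sites draw bloods that morning already, requiring it costs almost nothing.

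**Conclusion.** The concern holds. The required follow-up chemistry is thinnest at the first target dose: one post-dose value, at 4-8 hours, against two at every lower step. When the next dose is due, the last required value is 16-20 hours old, against at most 8 hours at lower steps. This applies to every patient who completes the ramp-up, in both phases.

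The result assumes dosing every 24 hours, management exactly as the text requires, and no weekly panel happening to fall that morning. The clinical size of the gap cannot be estimated from the documents. It is a design choice worth changing for patient safety, and it does not touch the statistical properties of the trial.

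**What to change.** Add one sentence to the Cycle 1 part of section 4.6: repeat the TLS panel on the morning after the first target dose (day 12, 13 or 14 at levels -1, 1 and 2; day 5, 6 or 7 with recent ponatinib exposure), with the result reviewed before that day's venetoclax, before discharge, and before any CYP3A inhibitor is started or resumed.

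The cost is one extra blood draw per patient within a stay already required. At two draws per step, ramp-up panels rise from 2 x 4 = 8, 2 x 5 = 10 and 2 x 6 = 12 to 9, 11 and 13. Discharge may wait a short time for the result.
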